4.3. Protocol Deviations

Subjects who did not meet the eligibility criteria for study entry, but enrolled in the study will be summarized regardless of whether they were exempted by the sponsor or not. The summary will present the number and percentage of subjects who did not meet at least 1 eligibility criterion and the number of subjects who did not meet specific criteria based on the All Enrolled Analysis Set or All Randomized Analysis Set. A by-subject listing will be provided for those subjects who did not meet at least 1 eligibility (inclusion or exclusion) criterion. The listing will present the eligibility criterion (or criteria if more than 1 deviation) that subjects did not meet and related comments, if collected.

Protocol deviations occurring after subjects entered the study are documented during routine monitoring. The number and percentage of subjects with important protocol deviations by deviation categories will be summarized for the All Enrolled Analysis Set or All Randomized Analysis Set. The deviation categories are as follows:

- IC=Informed consent
- EN=Eligibility Criteria
- XM=Excluded concomitant medication
- NW=Not withdrawn, despite meeting withdrawal criteria
- TA=Wrong treatment or incorrect dose
- TC=Other treatment compliance issue
- OS=Off schedule procedure
- MD=Missing data
- OT=Other

A by-subject listing will be provided for those subjects with important protocol deviation.

5. BASELINE CHARACTERISTICS

The following analyses will be presented by treatment group, phase, and dose level, treatment arm, or cohort if applicable, as elaborated in [Table 3-2](#) in [Section 3.2](#). Summaries will be provided for the FAS.

5.1. Demographics

Subject demographic variables (ie, age, sex, race, and ethnicity) will be summarized using descriptive statistics for age, and using number and percentage of subjects for sex, race, ethnicity, and age groups (<65 years vs ≥65 years; and the age group defined in [Section 3.4](#) if applicable).

A by-subject demographic listing will be provided.

5.2. Other Baseline Characteristics

Other baseline characteristics include body weight (in kg), height (in cm), body mass index (BMI; in kg/m²), bone marrow blasts (in %), ECOG performance status, cytogenetics (normal or abnormal), ELN risk group, de novo/secondary AML, MLL status, and molecular mutation assessment. Bone marrow blasts will be based on the blasts in bone marrow aspirate. If blasts in bone marrow aspirate are not available, blasts in bone marrow biopsy will be used. These baseline characteristics will be summarized using descriptive statistics for continuous variables and using number and percentage of subjects for categorical variables.

By-subject listings of other baseline characteristics will be provided.

5.3. Medical History

Medical history will be collected at screening for disease-specific and general conditions (ie, conditions not specific to the disease being studied).

A summary of disease-specific medical history will be provided. AML classification at screening will be presented by the FAB and the WHO classification subtypes. Subtypes will be summarized using summary statistics for a categorical variable. Time since AML diagnosis (weeks) will be calculated as (date of first dose of study drug – date of diagnosis)/7. Time since AML diagnosis will be summarized by using summary statistics for continuous variables.

General medical history data will not be coded.

By-subject listings of disease-specific and general medical history will be provided.

In deriving the time since AML diagnosis, partial dates of diagnosis will be identified, and the partial dates will be imputed as follows:

- If day and month are missing but year is available, then the imputed day and month will be 01 Jan.
- If day is missing but the month and year are available, then the imputed day will be the first day of the month.
- Partial date will not be imputed if the year is missing.

5.4. Prior Anticancer Therapy

For Group C, number of prior regimens and time since the completion of last regimen will be summarized using descriptive statistics. A partial completion date will be imputed using the algorithm defined in Section 5.3.

The prior anticancer therapies, the last regimens subjects received prior to study entry, and the best response to the last regimen will also be summarized.

6. EFFICACY ANALYSES

Assessment of clinical response will be made according to the International Working Group criteria for AML {Cheson 2003}, which is documented in Appendix 5 of the study protocol. The major criteria for judging response assessment include physical examination and examination of blood and bone marrow.

Efficacy analysis will be presented by treatment group, phase, and dose level, treatment arm, or cohort if applicable, as elaborated in Table 3-2 in Section 3.2. In addition, the pooled analyses of Group C for efficacy specified in Sections 6.1, 6.2, and 6.3 will be present by dose level and total as elaborated in Table 3-3 in Section 3.2. Summaries will be provided for the FAS.

6.1. Primary Efficacy Endpoints

6.1.1. Definition of the Primary Efficacy Endpoints

- Complete remission rate at induction completion: defined as the proportion of subjects who achieved morphologic complete remission (CR) at induction completion. Note that CR includes a subcategory of cytogenetic CR (CRc)
- Composite complete remission rate at induction completion: defined as the proportion of subjects who achieved morphologic complete remission (CR) or morphologic complete remission with incomplete blood count recovery (CRi) at induction completion
- Overall response rate at induction completion: defined as the proportion of subjects who achieved morphologic complete remission (CR), morphologic complete remission with incomplete blood count recovery (CRi), or partial remission (PR) at induction completion

6.1.2. Analysis of the Primary Efficacy Endpoints

Complete remission rate, composite complete remission (CR/CRi) rate, and overall response (CR/CRi/PR) rate at induction completion for Groups A and B will be summarized and the corresponding 95% exact CIs based on Clopper-Pearson method will be presented.

Response at induction completion is defined as the best response across the time points that occurred after day 1 of last cycle of induction therapy, and prior to the earliest of cycle 1 day 1 of post-remission or maintenance therapy, date of SCT and date of other anticancer therapy (excluding SCT and conditioning regimen (listed in Appendix 2)). Best response is the best outcome according to the ranking below by decreasing favorable level:

- 1) Cytogenetic Complete Remission [CRc]
- 2) Morphologic Complete Remission [CR]
- 3) Morphologic Complete Remission with Incomplete Blood Count Recovery [CRi]

- 4) Partial Remission [PR]
- 5) Morphologic Leukemia-free State [MLFS]
- 6) Relapse
- 7) Other

The category “Other” includes 3 subcategories: Treatment Failure [TF], Early Treatment Assessment [ETA], and No Assessment Done. For subjects who had response assessment in the last cycle but didn’t achieve any of the first 6 categories listed above at induction completion, TF will be the response at induction completion for those who received 2 induction cycles in Group A or received ≥ 2 induction cycles in Group B, and ETA will be the response at induction completion for those who only received ≤ 1 induction cycle. All subjects in “Other” will be considered as nonresponders and will be included in the denominator when calculating the remission rates at induction completion.

Complete remission rate, composite complete remission (CR/CRi) rate, and overall response (CR/CRi/PR) rate per best overall response ever achieved during the treatment for Group C will be summarized and the corresponding 95% exact CIs based on Clopper-Pearson method will be presented.

Best overall response is defined as the best response across all time points prior to SCT and other anticancer therapy (excluding SCT and conditioning regimen). Best response is the best outcome according to the ranking below by decreasing favorable level:

- 1) Cytogenetic Complete Remission [CRc]
- 2) Morphologic Complete Remission [CR]
- 3) Morphologic Complete Remission with Incomplete Blood Count Recovery [CRi]
- 4) Partial Remission [PR]
- 5) Morphologic Leukemia-free State [MLFS]
- 6) Other

The category “Other” includes 2 subcategories: Treatment Failure [TF] and No Assessment Done. All subjects in “Other” will be considered as nonresponders and will be included in the denominator when calculating the remission rates per best overall response.

As a sensitivity analysis, complete remission rate, composite complete remission (CR/CRi) rate, and overall response (CR/CRi/PR) rate per best overall response ever achieved during the treatment will be summarized for Groups A and B. The category “Other” includes 3 subcategories: Treatment Failure [TF], Early Treatment Assessment [ETA], and No Assessment Done. For subjects who had response assessment but didn’t achieve any of the first 5 categories

listed above as the best overall response, TF will be the best overall response for those who received 2 induction cycles in Group A or received ≥ 2 induction cycles in Group B, and ETA will be the best overall response for those who only received ≤ 1 induction cycle. All subjects in “Other” will be considered as nonresponders and will be included in the denominator when calculating the remission rates per best overall response.

As an example, assuming a subject in Group A received two induction cycles and discontinued all study drugs, if subject achieved PR at end of Cycle 1 but relapsed at end of Cycle 2, the best overall response is PR while the response assessment at induction completion is relapse.

When the date of initiation of SCT/anticancer therapy other than the study treatment is incomplete or missing, the following algorithm will be followed:

- If the day is missing but the month and year are available, then the imputed day will be the last day of the month.
- If day and month are missing but year is available, then the imputed day and month will be 01Jan or the last day of the month for the last adequate disease assessment if they have the same year, whichever is later.

The following subgroup analyses will be provided for primary analysis:

- Age (<60 years, ≥ 60 years; applicable to Groups A and C)
- Age (≤ 75 years, >75 years; applicable to Group B)
- ELN risk group (Favorable, Intermediate -I, Intermediate -II, Adverse)
- De novo and Secondary AML
- Age and ELN risk group (applicable to Group A)
- With and without MLL
- FLT3-ITD mutation (applicable to Groups A and B)
- NPM1 mutation (applicable to Groups A and B)

For Group B phase 2 randomization, similar analyses will be provided by randomization stratum if there is sufficient sample size in the subgroup. The denominator for the percentage of subjects in the stratum will be the total number of randomized subjects. If there are discrepancies in the value used for stratification assignment between the IWRS and the clinical database, the value collected in the clinical database will be used for the summary.

Data listings for the clinical responses will be presented.

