The investigator must consult the medical monitor if subjects have not obtained a CR after Cycle 1 and prior to Cycle 2, and if there is any consideration to omit Cycle 2 of induction chemotherapy.

Subjects with cytogenetic and molecular mutations at screening must have cytogenetic and molecular mutation testing repeated at subsequent bone marrow examinations (Cycle 0 Day 14, Cycle 1 Day 14, count recovery, End of Study).

Subjects will undergo a daily CBC from Cycle 1 Day 14 (ie, count nadir) until count recovery at which time a bone marrow aspirate and biopsy will be performed.

Once a CR/CRi is confirmed on a recovery bone marrow examination (ie, the subject achieves < 5% blasts by morphology and flow cytometry), the subject will proceed to either allogeneic stem cell transplantation (SCT) or post-remission chemotherapy with cytarabine.

If CR/CRi is not achieved by the end of Cycle 2, the subject will be considered a treatment failure and will have met study efficacy endpoint criteria, but will remain on study for required study-related follow-up procedures.

Entospletinib + cytarabine post-remission (at least 3 cycles, and up to 4 cycles):

Post-remission chemotherapy will be offered to eligible subjects who have achieved CR/CRi and do not require or cannot proceed to allogeneic SCT. In addition, subjects who are awaiting a donor or transitioning to allogeneic SCT will be allowed to receive post-remission chemotherapy per investigator discretion. Therapy will consist of 3g/m² high dose cytarabine administered IV every 12 hours on Days 1, 3, and 5 (< 60 years of age) or 1g/m² cytarabine administered once daily on Days 1-5 (≥ 60 years of age) in combination with 400 mg ENTO every 12 hours on Days 1-28 of each 28-day cycle.

[figure not shown]
Subjects in whom definitive post-remission chemotherapy is planned will receive at least 3 and up to 4 cycles of cytarabine. Subjects who are awaiting a donor or transitioning to SCT may receive at least 1 and up to 4 cycles of cytarabine.

A bone marrow aspirate sample will be collected for disease assessment and biomarker research at the end of every 2 cycles (Cycle 2 Day 28 and Cycle 4 Day 28) and at suspected disease progression. Subjects who continue to maintain a CR/CRi after 3-4 cycles of post-remission chemotherapy will be offered maintenance with ENTO 400 mg every 12 hours for up to 12 cycles.

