- Physical exam (Day 1 and at the Investigator's discretion after hospital discharge)
- Obtain smoking status for past 28 days (Day 1 of each cycle)
- 12-lead ECG (at the investigator's discretion)
- ECHO or MUGA prior to re-induction, if applicable (Note: For German sites, only ECHO to be performed)
- Urine pregnancy test (for all female subjects unless surgically sterile or menopausal prior to dose on Day 1)
- Obtain blood samples for:
 - Chemistry (Days 7 and 14)
 - Hematology (Days 7, 14, and up to blood count recovery)

— Coagulation (Days 7 and 14)

— PK

- Phase 1b (Dose Escalation): Cycle 1 Day 3 and Cycle 1 Day 7 at pre-dose, 2 hours, and 4 hours post-dose of ENTO; Cycle 1 Day 14 at pre-dose and 2 hours post-dose of ENTO
- Phase 2 (Dose Expansion): Cycle 1 Day 3 (and Cycle 2, if needed) at pre-dose, 2 hours, and 4 hours post-dose of ENTO; Intensive PK on Cycle 1 Day 7 at pre-dose, 1, 2, 3, 4, 6, 8, and 12 hours post-dose of ENTO; Cycle 1 Day 14 at pre-dose and 2 hours post-dose of ENTO

— Biomarkers (Cycle 1 Day 7 and Cycle 1 Day 14 or at the end of Cycle 1 at the time of blood count recovery at pre-dose)

Note: ENTO should be held until the pre-dose blood samples have been drawn. Record the approximate time of the last 2 doses of ENTO on PK collection days and the time the PK blood samples are obtained.

- Obtain bone marrow aspirate and biopsy samples on Cycle 1 Day 14 for disease assessment and biomarker testing. If the bone marrow is consistent with Morphologic CR or CRi status per [Appendix 5](#), evaluate MRD as per institutional practice and [Appendix 7](#). Biopsy will be used in the event the aspirate cannot be collected or analyzed (eg, dry-tap, hemodiluted specimen, or lack of spicules).
 - If the bone marrow cellularity is $\leq 20\%$ at Cycle 1 Day 14, a repeat bone marrow examination will occur within 2 weeks or at count recovery. Subjects with residual disease detected at the Cycle 1 Day 14 bone marrow evaluation will proceed with Cycle 2 of induction chemotherapy. The start of Cycle 2 will depend on the timing and result of the disease assessment. Subjects are to continue receiving ENTO while awaiting disease assessment results.
 - The investigator must consult the medical monitor if subjects have not obtained a CR after Cycle 1 and prior to Cycle 2, and if there is any consideration to omit Cycle 2 of induction chemotherapy.

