Appendix 5. International Working Group Criteria for AML {Cheson 2003}

Assessment of clinical response will be made according to the International Working Group criteria {Cheson 2003}. The major criteria for judging response will include physical examination and examination of blood and bone marrow. All laboratory studies that are abnormal prior to study will be repeated to document the degree of maximal response.

Early Treatment Assessment (ETA)

- Evaluation is made at approximately 7-10 days after completing the last dose of the initial course of treatment (ie, Group A Cycle 1 Day 14)
- Guides subsequent treatment (eg, need for or timing of second induction course)

Morphologic Leukemia-free State (MLFS)

MLFS requires all of the following:

- <5% blasts in bone marrow aspirate
- No extramedullary disease
- No blasts with Auer rods detected

Morphologic Complete Remission (CR)

CR requires all of the following:

- <5% blasts in bone marrow aspirate
- Neutrophils $\geq 1,000/\mu\text{L}$
- Platelets $\geq 100,000/\mu\text{L}$
- No extramedullary disease
- No blasts with Auer rods detected
- Independent of transfusions

Cytogenetic Complete Remission (CRc)

CRc requires all of the following:

- <5% blasts in bone marrow aspirate
- Neutrophils $\geq 1,000/\mu\text{L}$

- Platelets $\geq 100,000/\mu\text{L}$
- No extramedullary disease
- No blasts with Auer rods detected
- Independent of transfusions
- Reversion to a normal karyotype with an abnormal karyotype at the time of diagnosis

Morphologic CR with incomplete blood count recovery (CRi)

CRi requires all of the following:

- $< 5\%$ blasts in bone marrow aspirate
- Neutrophils $< 1,000/\mu\text{L}$ or Platelets $< 100,000/\mu\text{L}$
- No extramedullary disease
- No blasts with Auer rods detected

If blood counts recover within 14 days of a bone marrow evaluation that is consistent with CRi, the patient will be considered CR at the time when both neutrophil and platelet count recover (neutrophils $\geq 1,000/\mu\text{L}$, platelets $\geq 100,000/\mu\text{L}$).

Partial Remission (PR)

PR requires all of the following:

- $\geq 50\%$ decrease in blasts in bone marrow aspirate to a range of 5-25%
- Neutrophils $\geq 1,000/\mu\text{L}$
- Platelets $\geq 100,000/\mu\text{L}$
- Independent of transfusions
- A value of $\leq 5\%$ blasts may also be considered a PR if Auer rods are detected

Treatment Failure (TF)

Treatment failure will be classified as one of the following:

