- Resistant disease: Failure to achieve a complete remission (CR, CRc, or CRi) or partial remission. Patients who survive ≥ 7 days following completion of initial treatment, with evidence of persistent leukemia by blood and/or bone marrow examination.

- Death in Aplasia: Patients who survive ≥ 7 days following completion of initial treatment, but die while cytopenic, with an aplastic or hypoplastic marrow obtained within 7 days of death, without evidence of persistent leukemia
- Death from Indeterminate cause: Patients who die before completion of treatment or < 7 days following completion of initial treatment; patients who die ≥ 7 days following completion of initial treatment with no peripheral blood blasts, but no bone marrow examination is available; patients who fail to complete the first cycle of therapy

Relapse

Relapse is defined as:

- Evidence of morphologic relapse with the reappearance of leukemic blasts in the peripheral blood, blasts with Auer rods, $\geq 5\%$ blasts in the bone marrow, or evidence of extramedullary disease not attributable to any other cause. In the setting of recent treatment, if there are no circulating blasts and the bone marrow contains 5-20% blasts, a bone marrow biopsy should be repeated within 1 week to distinguish relapse from bone marrow regeneration.
- The reappearance of cytologically proven extramedullary disease also indicates relapse. Reappearance of a cytogenetic abnormality is considered a cytogenetic relapse. Evidence of bone marrow morphologic involvement or extramedullary disease required.

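### In Group A, the best-in-window rule of SAP 6.1.2 lets a Day 14 nadir marrow scored CRi outrank a later failing marrow or a death before recovery, which can raise the composite CR and overall response rates

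*SAP*

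**What the plan says.** **Endpoint rule (SAP 6.1.2, Groups A and B).** "Response at induction completion is defined as the best response across the time points that occurred after day 1 of last cycle of induction therapy". The sentence then sets where the window closes: "and prior to the earliest of cycle 1 day 1 of post-remission or maintenance therapy, date of SCT and date of other anticancer therapy". The ranking is CRc, CR, CRi, PR, MLFS, Relapse, Other. Treatment failure (TF) and early treatment assessment (ETA) sit in Other and are assigned only by default. For subjects assessed in the last cycle who did not "achieve any of the first 6 categories listed above at induction completion, TF will be the response at induction completion" if they had enough induction cycles; otherwise it is ETA. The one sensitivity analysis for these groups uses best overall response during treatment.

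**Response definitions (Protocol Appendix 5).** MLFS is under 5% marrow blasts, no extramedullary disease and no blasts with Auer rods. CRi is the same list plus low neutrophils or low platelets. CR needs both counts recovered and transfusion independence. A CRi becomes CR if counts recover within 14 days of the marrow. Treatment failure includes patients who "die while cytopenic, with an aplastic or hypoplastic marrow obtained within 7 days of death".

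**Day 14 in Group A.** Protocol 3.1.2 describes Cycle 1 Day 14 as the count nadir and sends subjects on to transplant or post-remission therapy "Once a CR/CRi is confirmed on a recovery bone marrow examination". Two other labels exist for that time point: ETA in Appendix 5, and an MLFS rate with its own analysis window in SAP 3.8.2 (Cycle 1 Day 1 + 13 ± 2 days).

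**The concern.** A marrow at the nadir is provisional: it may be empty because chemotherapy has just cleared it, and recovery shows whether leukemia returns with normal hematopoiesis. The protocol's treatment path respects this by waiting for a recovery marrow. The SAP endpoint does not carry that condition over. Because the rule keeps the best reading in the window, an early favorable reading cannot be overturned by a later unfavorable one in the same cycle.

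Any resulting error goes one way, upward, on two of the three primary efficacy endpoints of a single-arm cohort. Readers will set the composite rate beside the 52% quoted for 7+3.

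**Working it through.** **1. Can a Day 14 nadir marrow meet CRi?** As written, yes. Any marrow that meets MLFS while neutrophils or platelets are low also meets CRi, and low counts are what a nadir means. No rule says which label takes precedence at Day 14. The hematology footnote to the Group A Phase 2 schedule (Protocol Appendix 2) asks for counts from a CRi marrow until recovery or 14 days, so CRi is expected to be called before counts recover.

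**2. What does SAP 6.1.2 then return?** Each case starts from a blast-free Day 14 marrow with low counts.

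| Course | Result under SAP 6.1.2 | Counts in composite CR? |
|---|---|---|
| Scored CRi in last cycle; recovery marrow fails; no further cycle | CRi | Yes |
| Scored CRi in last cycle; dies before recovery | CRi | Yes |
| Scored MLFS or ETA in last cycle; recovery marrow fails | MLFS or lower, or PR if PR criteria are met | No |
| Scored CRi in Cycle 1; Cycle 2 then given | Cycle 1 reading leaves the window; Cycle 2 decides | Depends on Cycle 2 |
| Scored CRi; recovery marrow confirms CR or CRi | CR or CRi | Yes, correctly |

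The first two rows are the problem. The SAP's worked example (PR in Cycle 1, relapse in Cycle 2) compares different cycles and does not settle two readings within one cycle. Best overall response draws on at least as many time points, so that sensitivity analysis is no stricter.

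**3. Who is exposed?** Group A subjects who receive no Cycle 2, those who die after Cycle 1, and those with a nadir reading in Cycle 2 (SAP 1.2 foresees a Cycle 2 marrow). Group B's scheduled induction marrows are at Day 28 of Cycles 2 and 4. Group C uses best overall response by design. Neither shares this path.

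**4. Size per affected subject.** Inputs: n = 40 for Group A Phase 2 and exact 90% intervals (Protocol 8.9, Table 8-1; SAP 1.3, Table 1-2); exact 95% Clopper-Pearson intervals for the analysis (SAP 6.1.2).

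Formula: lower = Beta quantile(α/2; x, n − x + 1); upper = Beta quantile(1 − α/2; x + 1, n − x).

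The plan's 90% table reproduces:
- 28/40: 56.0–81.7% (stated 56–82%)
- 32/40: 66.8–89.6% (stated 67–90%)
- 36/40: 78.6–96.5% (stated 79–97%)

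One subject is 1/40 = 2.5 points. Starting from 28/40, the plan's 70% case:

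| Subjects removed | Rate | Exact 90% CI | Exact 95% CI |
|---|---|---|---|
| 0 | 70.0% | 56.0–81.7% | 53.5–83.4% |
| 1 | 67.5% | 53.4–79.6% | 50.9–81.4% |
| 2 | 65.0% | 50.8–77.4% | 48.3–79.4% |
| 4 | 60.0% | 45.8–73.1% | 43.3–75.1% |

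At this observed rate, one reclassified subject takes the 95% lower bound below 52%, and two take the 90% lower bound below it.

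**The case against.** The strongest reply is that the problem arises only if sites score Day 14 marrows as CRi, and the documents point partly the other way. Appendix 5 names Group A Cycle 1 Day 14 as the early treatment assessment. The MLFS window in SAP 3.8.2 would have little purpose if every blast-free nadir marrow were CRi. This stands, and it is why the rates can be inflated rather than are inflated. It does not remove the point, because the definitions overlap and a primary endpoint should not depend on which label a site prefers.

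The protocol also narrows the path. Marrow cellularity of 20% or less at Day 14 calls for a repeat examination, the medical monitor must be consulted before Cycle 2 is omitted, and Cycle 2 resets the window. By-subject response and marrow listings would show affected cases. All of this lowers the likely number; none of it changes the ranking once a CRi is recorded.

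Several stronger readings are tempting and are not supported:

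- *Sites are told to score the Day 14 marrow for CR/CRi.* Protocol 6.3.1 says only "If the bone marrow is consistent with Morphologic CR or CRi status per" Appendix 5, evaluate MRD.
- *Deaths in aplasia are being counted as responses.* The rule allows it, but Protocol 1.3.1 reports 0% induction mortality at 30 days among 53 Group A subjects. Later deaths are not excluded.
- *EFS events are lost as well.* A CRi does remove the treatment-failure label in SAP 6.2.2, but Table 6-1 still counts death and recorded relapse within its windows.
- *The comparison with 7+3 is overturned.* No test against 52% is planned. The protocol calls that figure a composite CR rate and the SAP calls it a CR rate, so even the matching endpoint needs reconciling.
- *The open-ended window lets in very late responses.* Scheduled marrows stop at End of Study Treatment, so this has little practical effect.

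**Conclusion.** The point holds for Group A as a gap in the endpoint definition, and it should be fixed. As written, a nadir CRi in the last induction cycle outranks a later failing marrow or a death before recovery. Composite CR and overall response can therefore be biased upward. The CR-only rate is not affected by a nadir CRi as such; a CRi that becomes CR because counts recover within 14 days is CR under Appendix 5 and is not in dispute.

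The supportable size is 2.5 points per affected subject in a cohort of 40, with the number of such subjects unknown. A reader might infer a percentage-point range by assuming how many subjects fail at recovery and what share had a blast-free Day 14 marrow. The documents give neither quantity, and such a calculation would also have to remove subjects whose window is reset by Cycle 2. The conclusion assumes only that at least some Day 14 marrows may be scored CRi, which the definitions permit.

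**What to change.** Amend SAP 6.1.2 for Group A:

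1. Marrows in the Day 14 window of SAP 3.8.2, and the equivalent window in Cycle 2, with unrecovered counts are classed MLFS or ETA and do not by themselves count as CRi.
2. CR/CRi at induction completion rests on the recovery marrow, or otherwise the last later marrow, of the last induction cycle before the next therapy, in line with Protocol 3.1.2.
3. Death before that marrow is non-response.
4. A subject whose only marrow falls in the Day 14 window is classed MLFS or ETA, unless counts meet CR at that marrow or recover within the 14 days Appendix 5 allows. This must be explicit; otherwise using the last marrow and setting aside Day 14 marrows would conflict for that subject.
5. Keep the present best-in-window rule as a sensitivity analysis.

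The cost is SAP wording and one programming rule. Marrow schedules and treatment do not change. The composite CR rate may be slightly lower. SAP Section 1 places SAP finalization before database finalization, so the rule belongs there; a change after SAP finalization would have to be documented in the CSR.
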